### **3.5. Study Treatments**

Up to 250 subjects will be randomized in a 1:1 ratio to receive filgotinib 200 mg once daily or placebo once daily.

### **3.6. Duration of Treatment**

The duration of blinded treatment is approximately 13 weeks followed by an open-label Extension Phase of up to 143 weeks. Subjects entering the Monitoring Phase will be followed for up to 52 weeks or until Reversibility (see [Definition of Terms](#)) is met, whichever is achieved first.

### **3.7. Criteria for Interruption or Discontinuation of Study Treatment**

#### **3.7.1. Study Drug Interruption Considerations**

The Sponsor Medical Leader or designee should be consulted prior to study drug interruption when medically feasible. Study drug interruption should be considered in the following circumstances:

- Intercurrent illness that would, in the judgment of the investigator, affect assessments of clinical status to a significant degree.
- Subject is scheduled for elective or emergency surgery (excluding minor skin procedures under local or no anesthesia); timing of study drug interruption should be determined in consultation with the Sponsor Medical Leader or designee.
- Any subject who develops a new infection during the study should undergo prompt and complete diagnostic testing appropriate for an immunocompromised individual, and the subject should be closely monitored.
- After becoming aware of a laboratory change representing moderate renal failure (estimated creatinine clearance [CrCl]  $\geq 35$  mL/min and  $<60$  mL/min per Cockcroft-Gault [CC&G] formula) at any time during the study, the following actions should be taken and documented:
  - Establish possible underlying condition and initiate appropriate action to resolve.
  - Retest CrCl within 8 weeks.

- Carefully consider individual benefit/risk of continuation of filgotinib 200 mg once daily in relation to the observation.
- If continuation of filgotinib 200 mg once daily is not considered appropriate, interrupt treatment until retest confirms CrCl  $\geq 60$  mL/min.
- The principal investigator/deputy should assess individual patient benefit/risk with regards to re-initiation of treatment after repeat or prolonged interruptions, or if re-initiation is not considered appropriate. Consultation with the Sponsor medical monitor or designee is preferred in these situations.

During the time of study drug interruption, subjects are to continue with study visit participation and complete study procedures and assessments, deemed medically appropriate by the investigator.

After study drug interruption, prior to resumption of study drug, the investigator should discuss the case with the Sponsor Medical Leader or designee.

### **3.7.2. Study Drug Discontinuation Considerations:**

The Sponsor Medical Leader or designee should be consulted prior to study drug discontinuation when medically feasible.

Study drug should be permanently discontinued in the following instances:

- Any opportunistic infection
- Any serious infection that requires parenteral/intravenous antimicrobial therapy or hospitalization, or any infection that meets serious adverse event (SAE) reporting criteria.
- Febrile neutropenia (temperature  $>38.3^{\circ}\text{C}$  or a sustained temperature of  $>38^{\circ}\text{C}$  for more than 1 hour) with absolute neutrophil count of  $<1,000/\text{mm}^3$
- Symptomatic anemia (eg, signs/symptoms including pallor, shortness of breath, new heart murmur, palpitations, lethargy, fatigue) with hemoglobin  $<7.5$  g/dL, or if transfusion is indicated regardless of hemoglobin value
- Complicated herpes zoster infection (with multi-dermatomal, disseminated, ophthalmic, or CNS involvement)
- Evidence of active Hepatitis C virus (HCV) during the study, as evidenced by HCV RNA positivity
- Evidence of active Hepatitis B virus (HBV) during the study, as evidenced by HBV deoxyribonucleic acid (DNA) positivity
- Any thromboembolic event that meets SAE reporting criteria

- Unacceptable toxicity, or toxicity that, in the judgment of the investigator, compromises the ability to continue study specific procedures or is considered to not be in the subject's best interest
- A  $\geq 50\%$  decrease from Baseline (based on the mean of 2 separate semen samples collected at the Screening Visit) in sperm concentration and/or motility and/or morphology
- Subject request to discontinue for any reason
- Subject noncompliance to the protocol
- Discontinuation of the study at the request of the Sponsor, a regulatory agency or an institutional review board or independent ethics committee (IRB/IEC)
- Subject's use of prohibited concurrent therapy will trigger study discontinuation; consultation should be made with the Sponsor Medical Leader or designee
- Subjects with newly positive (converted) QuantiFERON® TB test (or centrally reported equivalent assay) and/or any subject with active TB
- Any of the below described abnormal laboratory changes occurring at any one time, and confirmed by repeat testing ([Appendix 11](#)):
  - 2 sequential neutrophil counts  $<0.75 \times 10^9$  cells/L (750 neutrophils/mm^3)
  - 2 sequential platelet counts  $<75.0 \times 10^9$  cells/L (75,000 platelets/mm^3)
  - 2 sequential aspartate aminotransferase (AST) or alanine aminotransferase (ALT) elevations  $>3x$  the upper limit of normal (ULN) and at least 1 of the following confirmed values: a) total bilirubin  $>2x$  ULN, b) international normalized ratio (INR)  $>1.5$ , or c) accompanied by symptoms consistent with hepatic injury. For any subject with an initial AST or ALT elevation  $>3x$  the ULN, at the time of the second confirmatory draw, an INR, prothrombin time (PT) and partial thromboplastin time (PTT) must also be drawn.
  - 2 sequential AST or ALT elevations  $>5x$ ULN
  - 2 sequential values for estimated CrCl  $<35$  mL/min based on the CC&G formula
- Subjects who permanently stop study drug due to pre-specified decrease in sperm parameters ([Section 6.11](#)) will be offered standard of care as part of the Monitoring Phase.
- Subjects who are unblinded prior to Week 13.

### **3.7.3. Study Discontinuation**

Subjects withdrawing from the study should make every effort to complete an ET visit; for subjects on blinded treatment or on filgotinib, this will be followed by a safety follow-up visit 30 days after last dose of study drug.

Subjects are free to withdraw from the study at any time without providing reason(s) for withdrawal and without prejudice to further medical treatment. The reason(s) for withdrawal will be documented in the electronic case report form (eCRF).

Reasonable efforts will be made to contact subjects who are lost to follow-up. All contacts and contact attempts must be documented in the subject's file.

The Sponsor has the right to terminate the study at any time in case of safety concerns or if special circumstances concerning the study drug or the company itself occur, making further treatment of subjects impossible. In this event, the investigator(s) and relevant authorities will be informed of the reason for study termination.

### **3.8. End of Study**

End of Study is reached when the last scheduled study visit occurred. This can be a Week 156 visit, a Follow-up visit, or the last visit of a Monitoring Phase.

### **3.9. Post-Study Care**

Upon completion of study participation, the long-term care of subjects will remain the responsibility of their primary treating physician.

## **4. SUBJECT POPULATION**

### **4.1. Number of Subjects and Subject Selection**

Up to 250 subjects with active RA, PsA, AS or nrAxSpA will be randomized in the study to ensure 200 subjects are evaluable at Week 13. Enrollment may be expanded if the dropout rate is higher than expected and will be evaluated during the course of the study.

### **4.2. Inclusion Criteria**

Subjects must meet all of the following inclusion criteria to be eligible for participation in this study.

- 1) Able to understand and willing to sign the informed consent as approved by the IRB/IEC. Written consent must be provided before initiating any Screening evaluations. Subjects must have read and understood the ICF, must fully understand the requirements of the study, and must be willing to comply with all study visits and assessments; subjects who cannot read or understand the ICF may not be enrolled in the study by a guardian or any other individual
- 2) Male between the ages of 21 and 65 (inclusive) on the day of signing informed consent

3) Body mass index (kg/m^2) of  $\geq 18.5$  to  $\leq 40$  at Screening, with no evidence of malnutrition as determined by the investigator

4) Diagnosis of RA, PsA, AS, or nrAxSpA for at least 12 weeks prior to Screening, meeting the corresponding specific classification criteria:

- RA, ACR/ European League Against Rheumatism (EULAR) 2010
- PsA, Classification criteria for Psoriatic Arthritis (CASPAR) criteria
- AS or nrAxSpA, Assessment of Spondyloarthritis International Society (ASAS) criteria for axial spondyloarthritis

5) For RA, PsA, AS, or nrAxSpA, meets the following criteria:

- RA
  - Inadequate response or intolerant to an  $\geq 12$ -weeks' course of csDMARD or bDMARD therapy for RA
  - Have an CDAI  $> 10$  at Screening
- PsA
  - Inadequate response or intolerant  $\geq 12$ -weeks' course of csDMARD or bDMARD therapy for PsA
  - Have a Disease Activity in Psoriatic Arthritis (DAPSA) score  $> 14$  at Screening
- Axial Spondyloarthritis (applicable to those with diagnosis of AS or nrAxSpA)
  - Inadequate response or intolerant to at least 2 NSAIDs, which may include cyclooxygenase-2 (COX-2 inhibitors) prescribed for a total period of  $\geq 4$  weeks OR to an at least 12-weeks' course of csDMARD or bDMARD therapy for spondyloarthritis
  - Have a BASDAI  $\geq 4$  at Screening
  - At Screening, subjects should have a high-sensitivity C-reactive protein (hsCRP)  $> 0.3$  mg/dL OR sacroiliitis according to the modified New York (NY) criteria OR a history of active inflammation on magnetic resonance imaging (MRI) consistent with sacroiliitis within 2 years of screening

6) If using csDMARD therapy, subjects are permitted to use one of the following drugs, alone or in combination (with the exception of the MTX-LEF combination) and must have been on a stable dose of the drug for at least 4 weeks prior to Screening and remain on a stable dose during the Double-blind Treatment Phase of the study (stable dose in all cases is defined as no change in prescription):

- a) MTX oral or parenteral up to 25 mg/week (plus concomitant use of folic or folinic acid supplementation as per local Standard of Care)
- b) Leflunomide (LEF) up to 20 mg/day orally
- c) Hydroxychloroquine up to 400 mg/day or chloroquine up to 250 mg/day orally
- d) Apremilast orally up to 30 mg twice daily

Note that SSZ is not permitted at any time, beginning 26 weeks prior to Screening until the end of the study, and cannot be included in the Standard of Care arthritis regimen, due to its potential impact on semen parameters.

- 7) The mean of 2 separate semen samples collected at Screening must meet the following minimum criteria (in accordance with Section 6.11): semen volume  $\geq$ 1.5 mL, total sperm per ejaculate  $\geq$ 39 million, sperm concentration  $\geq$ 15 million per mL, sperm total motility  $\geq$ 40% and normal sperm morphology  $\geq$ 30%
- 8) LH, FSH, inhibin B, and total testosterone values within 20% of laboratory reference ranges during Screening
- 9) Subjects who engage in heterosexual intercourse must agree to use protocol-specified method(s) of contraception as described in [Appendix 10](#) including use of condoms during the study and for 90 days after the last dose of study drug
- 10) Willingness to refrain from receiving live and attenuated vaccines within 30 days of Day 1, throughout the study, and for 12 weeks after the last dose of study drug (Section 5.4, Vaccine Guidelines).
- 11) Meet one of the following 3 TB Screening criteria:
  - a) No evidence of active or latent TB:
    - A negative QuantiFERON® TB-Gold Plus In-Tube test at Screening, AND
    - A chest radiograph (views as per local guidelines) taken at Screening or within the 3 months prior to Screening (with the report or films available for investigator review) without evidence of active or latent TB infection, AND
    - No history of either untreated or inadequately treated latent TB infection
  - b) Previously treated for TB:
    - A subject who has previously received an adequate course of therapy as per local standard of care for either latent TB (e.g. 9 months of isoniazid in a location where rates of primary multi-drug resistant TB infections are  $<5\%$ , or an alternative regimen according to local country guidelines) or active TB (acceptable multi-drug regimen).

In these cases, no QuantiFERON® TB-Gold PLus In-Tube test (or a centrally reported equivalent assay) needs to be obtained.

- A chest radiograph must be obtained if not done within 3 months prior to Screening (with the report or films available for investigator review).
- It is the responsibility of the investigator to verify the adequacy of previous anti-TB treatment and provide appropriate documentation.

c) Newly identified latent TB during Screening:

- A subject who has a newly identified positive diagnostic TB test result (defined as a positive QuantiFERON® TB-Gold Plus In-Tube test or equivalent assay) in which active TB has been ruled out and for which appropriate, ongoing treatment for latent TB has been initiated for at least 4 weeks prior to the first administration of study drug.
- Adequate treatment for latent TB is defined according to local country guidelines for immunocompromised patients.

Cases falling under category “b” and “c” must be approved by the Sponsor Medical Leader or designee prior to enrollment in the study. No subject with currently active or untreated latent TB may be enrolled in the study. If a subject had a QuantiFERON® TB-Gold Plus In-Tube test for the purposes of clinical care or for the purpose of Screening for another Galapagos- or Gilead-sponsored study within 60 days, the prior result may be used to assess eligibility.

12) Laboratory parameters need to be met as per below:

- a) Hepatic panel (AST, ALT, total bilirubin)  $\leq 2 \times$  the ULN
- b) Estimated CrCl  $\geq 40$  mL/min as calculated by the CC&G equation
- c) Hemoglobin  $\geq 8$  g/dL
- d) Absolute neutrophil count (ANC)  $\geq 1.5 \times 10^9/L$  (1,500/mm^3)
- e) Platelets  $\geq 100 \times 10^9/L$
- f) White blood cells (WBC)  $\geq 3.0 \times 10^9/L$
- g) Absolute Lymphocyte count  $>750/\text{mm}^3$

### 4.3. Exclusion Criteria

Subjects who meet *any* of the following exclusion criteria are not to be enrolled in this study (Note: "Screening" refers to the first day of Screening).

- 1) Previously documented problems with male reproductive health including, but not limited to, known hypothalamic-pituitary disorders (e.g. pituitary macroadenomas, pituitary infarction, hyperprolactinemia, panhypopituitarism), primary hypogonadism (e.g. cryptorchidism, Klinefelter's syndrome)
- 2) Prior diagnosis of male infertility (including reduced fertility), or history of anti-sperm antibodies
- 3) Clinically significant (per judgment of investigator) varicocele or spermatocele
- 4) History of radiation to the testicles
- 5) History of clinically significant trauma to, or surgery on, the testicles, including vasectomy
- 6) Current treatment with antiandrogen therapy (including but not limited to spironolactone, oral ketoconazole, or cyproterone acetate), or treatment within 4 weeks of Screening
- 7) Current treatment with testosterone replacement therapy, or treatment within 12 weeks of Screening
- 8) Current treatment with 5- $\alpha$  reductase inhibitors (including but not limited to finasteride and dutasteride), or treatment within 4 weeks of Screening
- 9) Current treatment with alpha-1 blockers (including but not limited to tamsulosin, doxazosin, prazosin), or treatment within 4 weeks of Screening
- 10) Current use of SSZ or use of SSZ within 26 weeks of Screening; SSZ is not permitted at any point during the study
- 11) Current use of with alkylating agents or any recognized testicular toxin, or treatment within 26 weeks prior to Screening (may be discussed with Sponsor Medical Leader or designee)
- 12) Current treatment with TNF $\alpha$  antagonist (including but not limited to infliximab, adalimumab, etanercept, golimumab, certolizumab, and biosimilar agents), or treatment within 4 weeks of Screening
- 13) Use of any prohibited concomitant medication(s) as described in Section 5.3)
- 14) Known hypersensitivity to filgotinib, its metabolites, or formulation excipients
- 15) Presence of disorders of sperm transport including, but not limited to retrograde ejaculation and immotile cilia syndrome

- 16) Clinically significant urinary tract infection, prostatitis, epididymitis, including sexually transmitted infection within 4 weeks of Screening
- 17) Positive urine test for amphetamines or cocaine; positive test to opioids without a prescription, or heavy tobacco use (current use of  $\geq 2$  packs per day equivalent)
- 18) Uncontrolled thyroid dysfunction (eg, untreated hypothyroidism or hyperthyroidism)
- 19) Any sexual dysfunction of a nature that would prevent sperm collection in accordance with protocol guidance (phosphodiesterase inhibitors, however, are permitted during the study)
- 20) History of major surgery or trauma within 30 days prior to Screening, or anticipated need for major surgery during the study
- 21) Vaccination with live attenuated vaccine(s) within 30 days of Day 1 (see also Section 5.4, Vaccine Guidelines)
- 22) A positive test result for human immunodeficiency virus (HIV)-1 or HIV-2 (See Appendix 12)
- 23) Evidence of active HCV infection. Subjects with positive HCV antibody (Ab) at Screening, require reflex testing for HCV RNA. Subjects with positive HCV RNA at Screening will be excluded. Subjects with positive HCV Ab, but negative HCV RNA are eligible per investigator judgment. Subjects with active HCV during the study, as evidenced by HCV RNA positivity will be discontinued from study drug as outlined in the protocol.
- 24) Evidence of active HBV infection. Subjects with positive Hepatitis B surface antigen (HBsAg) at Screening are excluded from the study. Subjects with positive HBV core Ab and negative HBsAg, require reflex testing for HBV DNA. Subjects with positive HBV DNA at Screening will be excluded. Subjects with positive HBV core Ab and negative HBV DNA are eligible per investigator judgment, but may require prophylactic treatment in accordance with HBV treatment guidelines/local standard of care and require ongoing monitoring with blood tests for HBV DNA every 3 months. Subjects with evidence of active hepatitis B during the study, as evidenced by HBV DNA positivity, will be discontinued from study drug as outlined in the protocol.
- 25) Presence of Child-Pugh Class C hepatic impairment
- 26) History of malignancy within the past 5 years prior to Screening, (exception will be made for adequately treated basal cell carcinoma or non-metastatic squamous cell carcinoma of the skin, with no evidence of recurrence)
- 27) History of lymphoproliferative disorder, lymphoma, leukemia, myeloproliferative disorder, or multiple myeloma
- 28) History of leukocytapheresis  $\leq 6$  months prior to Screening

29) Any chronic medical condition (including, but not limited to, cardiac or pulmonary disease, or substance abuse) or psychiatric problem that, in the opinion of the investigator, would make the subject unsuitable for the study or would prevent compliance with the study protocol procedures

30) Active clinically significant infection, or any infection requiring hospitalization or treatment with intravenous anti-infectives within 30 days of Screening (or 8 weeks of Day 1); or any infection requiring oral anti-infective therapy within 2 weeks of Screening (or 6 weeks of Day 1)

31) History of opportunistic infection or immunodeficiency syndrome

32) Currently on any systemic (oral or intravenous) anti-infective therapy for chronic infection (such as pneumocystis pneumonia [PCP], cytomegalovirus (CMV), herpes zoster, atypical mycobacteria)

33) History of disseminated *Staphylococcus aureus* infection

34) History of symptomatic herpes zoster or herpes simplex within 12 weeks of Screening, or any history of disseminated herpes simplex, disseminated herpes zoster, ophthalmic zoster, or CNS zoster

35) Participation in any clinical study of an investigational device within 30 days, investigational non-biologic drug within 30 days, or investigational biologic drug within 8 weeks (or 5 half-lives, whichever is longer), prior to Screening.

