**Applicable Section:** [9.1.7](#) IMP Accountability and Return

**Rationale:** A footnote was added to provide more details on the Safety follow-up visit.

**Applicable Section:** Appendix 2, Study Procedure Table – Double-blind Treatment Phase

**Rationale:** The 12-lead ECG assessment has been removed in (the last scheduled visit of) the Monitoring Phase since the patient is not on filgotinib anymore; therefore, this assessment is not needed for safety reasons.

**Applicable Section:** Appendix 2, Study Procedure Table - Monitoring phase

**Rationale:** Footnotes have been updated for accurateness and to avoid confusion.

**Applicable Section:** Appendix 2, Study Procedure Table - Extension phase

**Rationale:** Text was added to specify that in the Extension Phase ECG for safety assessment is only required for subjects on study drug (open-label filgotinib) and not for subjects on Standard of Care treatment. The ECG in subjects on Standard of Care treatment is seen as redundant and therefore removed to reduce the patient burden.

**Applicable Section:** Appendix 2, Study Procedure Table - Extension phase

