### 3.2. Extension Phase

**Figure 3-3. Extension Phase – Evaluation**

\*Open-label treatment with filgotinib or Standard of Care. Adjustment of background treatment with non-prohibited medication allowed at any time during the Extension Phase

In the Extension Phase, subjects will receive open-label treatment (filgotinib or Standard of Care) and have a study visit every 13 weeks that includes semen analysis. The first scheduled visit of the Extension Phase occurs at Week 26.

In case sperm parameters at any visit (including Week 156) meet any of the pre-specified decrease thresholds, subjects will enter the Monitoring Phase.

During the Extension phase, Standard of Care and background treatment concomitant to filgotinib may be optimized at the discretion of the investigator, taking into consideration the protocol restrictions.

[figure not shown]
In case a subject needs to be treated with a prohibited medication (see [Table 5-1](#)), for instance to control their rheumatic condition, the subject will discontinue the study and complete an Early Termination (ET) visit (including semen collection). For subjects on filgotinib, this will be followed by a safety follow-up visit 30 days after last study drug dose.

All subjects who did not enter the Monitoring Phase will continue the study until the Week 156 visit.

In the Extension Phase, subjects must have yearly Quantiferon® testing. Yearly TB testing begins 1 year from the screening TB test date. If yearly TB testing falls between study visits, the yearly TB testing should be performed at the visit prior to 1 year from the screening TB test date. Subjects with newly positive (converted) Quantiferon® (or centrally reported equivalent assay) TB test should be discontinued from the study. Subjects who were previously treated for TB with a complete and adequate course of therapy as per local Standard of Care and as verified by the investigator do not need to have yearly tests.

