### 3.3. Monitoring Phase (up to 52 weeks)

Figure 3-4. Monitoring Phase - Evaluation

\*Adjustment of background treatment with non-prohibited medication allowed at any time during the Monitoring Phase

Subjects whose sperm parameters meet any of the pre-specified decrease thresholds will switch to the Monitoring Phase immediately. Subjects on double-blinded treatment or open-label filgotinib who enter the Monitoring Phase will discontinue study drug and start Standard of Care. These subjects will also have a safety follow-up visit 30 days after last study drug dose. Subjects on Standard of Care will continue treatment.

All subjects who enter the Monitoring Phase will undergo semen evaluations every 13 weeks starting from their entry into the Monitoring Phase, for up to 52 weeks or until Reversibility (see [Definition of Terms](#)) is met, whichever is achieved first.

In case a subject needs to be treated with a prohibited medication (see [Table 5-1](#)), for instance to control their rheumatic condition, the subject will discontinue the study and complete an ET visit (including semen collection).

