## **6.6. Monitoring Phase**

Subjects on filgotinib who enter the Monitoring Phase will discontinue study drug and start Standard of Care. Subjects on Standard of Care will continue treatment.

All subjects who enter the Monitoring Phase will undergo semen evaluations every 13 weeks starting from their entry into the Monitoring Phase, for up to 52 weeks or until Reversibility (see [Definition of Terms](#)) is met, whichever is achieved first.

Study assessments will be completed as specified in the Study Procedures Table ([Appendix 2](#)).

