i The Screening semen sample collection should coincide with the Day 1 (Baseline) visit as much as possible. Semen samples will be collected on the visit day and/or as soon as possible after the visit day.

j Semen collection will be completed at ET visit only if previous semen samples were not collected within 2 weeks of ET.

k This question will be asked prior to each semen collection.

l An HIV-1/HIV-2 antigen/antibody test, a Hepatitis C virus antibody test, a Hepatitis B surface antigen, a Hepatitis B surface antibody and a Hepatitis core antibody test will be conducted on all subjects; Subjects with positive Hepatitis B surface antigen (HBsAg) at Screening are excluded from the study. Subjects with positive HBV core Ab and negative HBsAg, require reflex testing for HBV DNA. Subjects with positive HBV DNA at Screening will be excluded. Subjects with positive HBV core Ab and negative HBV DNA are eligible per investigator judgment, but may require prophylactic treatment in accordance with HBV treatment guidelines/local standard of care and require ongoing monitoring with blood tests for HBV DNA every 3 months. Subjects with evidence of active Hepatitis B during the study, as evidenced by HBV DNA positivity, will be discontinued from study drug as outlined in the protocol. Subjects with positive HCV antibody (Ab) at Screening, require reflex testing for HCV RNA. Subjects with positive HCV RNA at Screening will be excluded. Subjects with positive HCV Ab, but negative HCV RNA are eligible per investigator judgment.

m Subjects with positive HBV core Ab and negative HBV DNA at Screening require ongoing monitoring with blood tests for HBV DNA every 3 months.

n The subject will take the first dose (Day 1) in the clinical study center. For PK collection purposes, at Weeks 2 and 13, subjects should be instructed not to take their study drug, but rather to bring it with them to the clinic. Subjects will be instructed to take their dose during their scheduled visit, as detailed in Section [6.14](#).

o Only for subjects continuing on open-label filgotinib in the Extension Phase.

\*\* Week 13 visit must occur after 13 weeks of drug exposure. Therefore, visit window for this visit is +5 days. The end of the Double-Blind Treatment Phase is when the Week 13 semen results are available to the investigator and have been evaluated. Based on this evaluation, subjects are assigned to enter the Monitoring Phase or the Extension Phase.

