**Monitoring Phase (Section 6.6)**

EVENT	Monitoring Phase ( $\pm 5$ days)	ET
Study days (D)/weeks (W)	Visits occur every 13 weeks starting from their entry into the Monitoring Phase (for up to 52 weeks or until Reversibility is met, whichever is sooner)	
Symptom-directed Physical Exam, as needed	X	X
Vital Signs a and Weight	X	X
Urinalysis a	X	X
Hematology and Chemistry a	X	X
Serum hsCRP	X	
LH, FSH, inhibin B, total Testosterone a collection time between 07:00-11:00 in the morning	X	X
Concomitant Medications	X	X
Assessment of Adverse Events b	X	X
Semen Collection c (2 samples as per collection instructions in Section 6.11)	X	X e
Date and time of most recent ejaculation d	X	

a As detailed in [Appendix 12](#).

b As detailed in [Section 7.3](#).

c Semen samples will be collected every 13 weeks from the day of study drug discontinuation, for up to 52 weeks or until Reversibility is met, whichever is achieved sooner. Reversibility is met when all sperm parameter(s) qualifying the subject to enter the Monitoring Phase return(s) to greater than 50% of Baseline (ie, to greater than [0.50 x Baseline]).

d This question will be asked prior to semen collection not at the site visit.

e Semen collection will be completed at ET visit only if previous semen samples were not collected within 2 weeks of ET.

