- g Only applicable for subjects on filgotinib.
- h ECG will be performed at Week 156 or ET (for subjects on open-label filgotinib only).
- i A sparse plasma PK sample is collected at Week 26 prior to study drug administration (for subjects on open label filgotinib only). Please refer to Section [6.14](#) for details on study drug administration.
- j An HIV-1/HIV-2 antigen/antibody test, a Hepatitis C virus antibody test, a Hepatitis B surface antigen, a Hepatitis B surface antibody and a Hepatitis core antibody test will be conducted on all subjects; Subjects with evidence of active Hepatitis B during the study, as evidenced by HBV DNA positivity, will be discontinued from study drug as outlined in the protocol.
- k Subjects with positive HBV core Ab and negative HBV DNA at Screening require ongoing monitoring with blood tests for HBV DNA every 3 months.
- l Semen collection will be completed at ET visit only if previous semen samples were not collected within 2 weeks of ET.

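### Criterion 24 requires HBV DNA every 3 months in core-antibody-positive, DNA-negative men, but the Monitoring Phase table schedules it at 0 of up to 4 visits

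*Protocol*

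**What the plan says.** Protocol 4.3, criterion 24, excludes men with active hepatitis B. Men with positive core antibody and negative HBV DNA may enter at the investigator's judgement, but they "require ongoing monitoring with blood tests for HBV DNA every 3 months". The criterion adds that a man whose HBV DNA becomes positive stops study drug.

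Appendix 2 repeats the rule as a footnote to two of its three tables. Footnote m of the double-blind table reads "Subjects with positive HBV core Ab and negative HBV DNA at Screening require ongoing monitoring with blood tests for HBV DNA every 3 months", and footnote k of the Extension table says the same. Both tables have an HBV DNA row: it is marked at Week 13 in the first and in the column covering Weeks 26 to 156 in the second.

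For the Monitoring Phase, Section 6.6 says "Study assessments will be completed as specified in the Study Procedures Table". The table it points to says "Visits occur every 13 weeks starting from their entry into the Monitoring Phase", for up to 52 weeks or until Reversibility. It lists physical examination, vital signs and weight, urinalysis, hematology and chemistry, hsCRP, sex hormones, concomitant medications, adverse events, semen collection and time of last ejaculation. HBV DNA is not listed, and footnotes a to e do not mention it. The copy in SAP Appendix 1 has the same rows.

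**The concern.** The eligibility text creates a continuing duty, and the schedule that sites are told to follow drops it in one phase. A site working from the Monitoring table would omit a viral test that criterion 24 requires.

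The timing is awkward. Under Section 3.3, a man who enters Monitoring from blinded treatment or open-label filgotinib "will discontinue study drug and start Standard of Care". Table 5-1 bars TNF and interleukin antagonists only through the double-blind phase and, for men on open-label filgotinib, through the Extension Phase, so in Monitoring they are no longer barred. The oral corticosteroid ceiling on Standard of Care is 20 mg/day of prednisone equivalent, against 10 mg/day in the double-blind phase. A man at known risk of HBV reactivation could therefore start another immunosuppressant just as his scheduled viral test lapses.

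What is at stake is patient safety in a small subset. The primary endpoint, sample size and analyses are untouched.

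**Working it through.** **Inputs**

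- Required interval: every 3 months, no phase limit (Protocol 4.3, criterion 24).
- Monitoring visits: every 13 weeks for up to 52 weeks, window ±5 days (Appendix 2, Monitoring table).
- Extension visits: every 13 weeks from Week 26 to Week 156 (Appendix 2, Extension table).
- SAP Monitoring visits: Weeks 13, 26, 39 and 52 of that phase (SAP Table 3-5).

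**Visit count.** 52 / 13 = 4, which reproduces the four Monitoring visits in SAP Table 3-5. They fall at 13 × 7 = 91, 26 × 7 = 182, 39 × 7 = 273 and 52 × 7 = 364 days. Since 13 weeks is about 3 months, each visit would meet the required interval.

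**HBV DNA by phase**

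| Phase | Scheduled visits | HBV DNA |
|---|---|---|
| Double-blind, end of phase | Week 13 | marked |
| Extension | (156 − 26) / 13 + 1 = 11 | marked, footnotes j and k only |
| Monitoring | up to 4 | 0 |

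The Extension table uses one column for all its visits. Reading the mark as 11 of 11 relies on the 3-monthly footnote and on the absence of a footnote naming weeks, such as the lipid row has.

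**Tests not scheduled.** A man who meets Reversibility at the first Monitoring visit misses 13 / 13 = 1 test. A man who never meets it misses 52 / 13 = 4. Counted from entry, the longest stretch without a scheduled test is 364 days, or 364 + 5 = 369 with the window. The preceding test belongs to the Week 13 or Extension visit that triggered entry. Entry itself waits for the semen results, so the interval between tests is somewhat longer than the stretch counted from entry.

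**Is the omission explained by being off drug?** Three comparisons bear on this.

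- *ECG.* The off-drug reasoning is written down. The Summary of Changes for Amendment 1 removes the Monitoring ECG "since the patient is not on filgotinib anymore", and Extension footnote h matches: "ECG will be performed at Week 156 or ET (for subjects on open-label filgotinib only".
- *HBV DNA.* The Extension row carries no filgotinib-only footnote, so men on Standard of Care, already off study drug, are scheduled for the test. If one of them moves to Monitoring he continues Standard of Care (Section 3.3), yet the test disappears.
- *TB testing.* This is also absent from Monitoring, but its text is limited by phase in Section 3.2: "In the Extension Phase, subjects must have yearly". Criterion 24 has no such words.

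**The case against.** The strongest reply is that the Monitoring schedule is deliberately lighter. Section 7.3 narrows adverse event reporting there to procedure-related events and SAEs. Lipids, ECG and TB testing are also gone. The protocol's only stated response to positive HBV DNA is to stop study drug (criterion 24 and Section 3.7.2), and men in Monitoring have stopped it or were on Standard of Care already. Footnotes m and k belong to phase-specific tables and do not by themselves reach Monitoring. On this reading, infection surveillance was confined to the other two phases on purpose.

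Part of this stands. The two footnotes show only that the rule is scheduled elsewhere; the case rests on criterion 24. A positive result would no longer change study drug, so the test would serve HBV care and the choice of Standard of Care. The deliberate-reduction reading still fails for HBV DNA, because no text exempts these men and the Extension table keeps the test for men off drug.

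Other safeguards are real but do not schedule the test. Standard of Care must follow good clinical practice by definition. Criterion 24 allows for guideline-based prophylaxis. Chemistry with AST, ALT and bilirubin continues every 13 weeks. Appendix 11 lists reflex HBV DNA when indicated, Section 6.10 lets investigators add tests, and rituximab and other lymphocyte-depleting drugs remain barred to the end of the study. Section 9.1.8 also keeps the investigator bound by criterion 24, so what is missing is the schedule entry and not the requirement. Finally, Amendment 2 describes the study as advanced, so few Monitoring visits may remain to benefit.

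**Conclusion.** The inconsistency is real and minor. For men with positive core antibody and negative HBV DNA at Screening, the protocol requires a test every 3 months and schedules none at up to 4 Monitoring visits. Between 1 and 4 required tests go unscheduled per affected man who attends at least one Monitoring visit, with up to 364 days from entry uncovered.

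This assumes that criterion 24 means what it says, with no unstated limit to time on drug, and that sites follow the phase table as Section 6.6 instructs. The documents do not say how many such men were enrolled or entered Monitoring; the number could be 0. No endpoint, estimate or analysis depends on it.

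**What to change.** Add an HBV DNA row to the Monitoring Phase table in Protocol Appendix 2, marked at each 13-weekly visit, and attach the wording of Extension footnote k so that it applies only to men with positive core antibody and negative HBV DNA at Screening. Update the copy in SAP Appendix 1 for consistency; no analysis changes.

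If the sponsor instead intends testing to stop at Monitoring entry, criterion 24 should say so and give the reason, since men on Standard of Care in the Extension continue to be tested.

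The cost is one row and one footnote, and at most 4 assays per affected man at visits where hematology and chemistry are already drawn. Whether extra blood volume is needed cannot be judged, because sample handling is in a separate laboratory manual (Section 6.10). The change needs IRB/IEC approval (Sections 9.1.2 and 9.2.1), so it is best added to the next planned amendment.
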